## 12.3.3 Safety Analyses

AEs will be coded using MedDRA and categorized as either oral or non-oral by prior to database lock. The number of AEs/SAEs and the number of participants with AEs/SAEs will be listed and tabulated overall and by System Organ Class (SOC) and Preferred Term (PT). This will be repeated including only Oral AEs/SAEs.

Property of Haleon- Confidential

May not be used, divulged, published or otherwise disclosed without the consent of Haleon

HALEON

Protocol Number: 300058

## 12.3.4 Demographic and Baseline Characteristics

Demographics, Baseline characteristics (including DH diagnosis (self-diagnosed or diagnosed by dentist); use of anti-sensitivity toothpaste (current user, intermittent user or non-user); and frequency of DH symptoms (compiled from responses from the Screening Questionnaire and the OHQ), and oral hygiene habits (compiled from responses to the OHQ) will be summarized using descriptive statistics for the mITT population.

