### 3 STUDY OBJECTIVES AND ENDPOINTS

Table 3-1 Study Objectives and Endpoints

Objectives	Endpoints
Primary	
To describe changes in OHrQoL over 24 weeks use of an anti-sensitivity toothpaste containing 0.454% SnF 2 , as measured by the Dentin Hypersensitivity Experience Questionnaire (DHEQ-48: Total Score and Domain Scores), in a DH population.	Change from Baseline in DHEQ endpoints at Weeks 4, 8, 12, 16, 20 & 24.  Section 2  Total Score (Q1-34)  Individual Domain Scores Restrictions (Q1-4) Adaptation (Q5-16) Social Impact (Q17-21) Emotional Impact (Q22-29) Identity (Q30-34)
Secondary	
To describe changes in OHrQoL over 24 weeks use of an anti-sensitivity toothpaste containing 0.454% SnF 2 , as measured by the DHEQ-48 (other endpoints), in a DH population.	Change from Baseline in DHEQ endpoints at Weeks 4, 8, 12, 16, 20 & 24.
	Section 1  • Impact on Everyday Life (Q1-3)
	
 
Section 2
 
Global Oral Health Score (Q35)
 
Effect on Life Overall Score (Q36-39)
 

To summarize the individual DHEQ domain items of concern in a DH population before and after 24 weeks use of an anti-sensitivity toothpaste containing 0.454% SnF 2 .	
 
Baseline and Week 24:
 
Percentage (%) of participants who 'agree' (score 5-7) with each item (statement) in the 5 DHEQ domains (DHEQ Section 2, Q1-34).
 

To describe changes in the intensity of self-reported DH pain over 24 weeks use of an anti-sensitivity toothpaste containing 0.454% SnF 2 , as measured by a Numeric Pain Rating Scale (NPRS), in a DH population.	Change from Baseline in NPRS score at Weeks 1, 2, 4, 8, 12, 16, 20 & 24.
To describe participant satisfaction with the DH treatment (anti-sensitivity toothpaste containing 0.454% SnF 2 ), as measured by a Satisfaction Numeric Rating Scale (NRS).	Week 24: Satisfaction NRS score
To describe the oral hygiene habits of a DH population using an oral hygiene questionnaire (OHQ).	Baseline: OHQ responses

This study will be considered successful if a trend of improvement in OHrQoL is observed over the 24-week treatment period; however, it is expected that statistically significant improvements from Baseline will be observed in DHEQ endpoints, particularly DHEQ Total Score.

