4.2.2 Secondary Endpoints

- Change from Baseline in additional DHEQ endpoints at Weeks 4, 8, 12, 16, 20 & 24.
 - Section 1:
 - Impact on Everyday Life (Q1-3, individually)
 - Section 2:
 - Global Oral Health Score (Q35)
 - Effect on Life Overall Score (Sum Q36-39)
- Percentage (%) of participants who 'agree' (score 5-7) with each item (statement) in the 5 DHEQ domains (DHEQ Section 2, Q1-34) at baseline and week 24.
- Change from Baseline in NPRS score at Weeks 1, 2, 4, 8, 12, 16, 20 & 24.
- Satisfaction Numerical Rating Scale (NRS) at Week 24.
- Oral Hygiene Questionnaire (OHQ) responses at Baseline.

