4.3.3 Populations to be Analyzed

For the purposes of analysis, the following analysis sets are defined:

The Screened population will include participants who electronically sign the eIC and enter the screening process for assessment of inclusion and exclusion criteria.

The Enrolled population will include all participants who meet the inclusion/exclusion criteria as identified by their responses to the screening questionnaire.

HLN-003 Statistical Analysis Plan	
Page 12 of 17	Version 1.0

The Safety population will include all enrolled participants who complete at least one use of study product (at least one entry in Brushing Diary). Safety population will be used for the analysis of AEs.

The modified Intent-To-Treat (mITT) population will include all participants in the Safety population who have at least one post-baseline derived DHEQ Total Score. Efficacy data will be analyzed using the mITT population only.

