4.3.6 Demographics and Baseline Characteristics

Age (years) will be summarized as both a continuous and categorical (<=40 years, >40 years) variable. Gender, race, and ethnicity will be summarized for safety and mITT populations and listed for the safety population.

The following baseline characteristics will be derived and summarized for safety and mITT populations:

- DH diagnosis (from OHQ):
 - self-reported DH without previous diagnosis by a dentist
 - \circ self-reported DH with previous diagnosis by a dentist
- Use of anti-sensitivity toothpaste (from OHQ):
 - Non-users will include subjects who are not currently using a sensitivity toothpaste e.g., first-time user
 - Intermittent users will include subjects who sometimes use a sensitivity toothpaste
 - current users will include subjects who regularly (daily) use a sensitivity toothpaste
- Frequency of DH symptoms (from SQ):
 - Frequent = Several times a day, Once a day, Several times a week

	HLN-003 Statistical Analysis Plan
Page 13 of 17	Version 1.0

 Less Frequent=Once a week, Several times a month, once a month, less than once a month

All categorical responses to the Screening Questionnaire and Oral hygiene Questionnaire will be summarized for the safety and mITT populations and listed for the safety population.

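### The Baseline-only oral hygiene questionnaire is summarised only in sets that depend on later product use or follow-up, so some enrolled participants who completed it are in no OHQ summary

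*Protocol*

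**What the plan says.** Protocol section 3 gives the OHQ its own secondary objective, which is to describe the oral hygiene habits of a DH population. SAP 4.2.2 defines the endpoint as "Oral Hygiene Questionnaire (OHQ) responses at Baseline". Protocol 8.2.1 makes the OHQ one of the Baseline tasks and ships product only to those who finish all of them.

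The documents assign the OHQ to analysis sets in three places:

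- Protocol 12.3.4 (summary): "oral hygiene habits (compiled from responses to the OHQ) will be summarized using descriptive statistics for the mITT population".
- SAP 4.3.6 (summary): "All categorical responses to the Screening Questionnaire and Oral hygiene Questionnaire will be summarized for the safety and mITT populations". The same sentence lists the responses for the Safety set.
- SAP 4.3.14 (listing): the OHQ is placed with the mITT data. Demographic and baseline characteristics are listed for the Enrolled set.

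SAP 4.3.3 defines the sets. Enrolled is fixed at screening: "The Enrolled population will include all participants who meet the inclusion/exclusion criteria as identified by their responses to the screening questionnaire". Safety is "all enrolled participants who complete at least one use of study product (at least one entry in Brushing Diary"). The mITT set is the part of Safety "who have at least one post-baseline derived DHEQ Total Score".

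**The concern.** A description of habits at Baseline needs only the Baseline answer. Both planned summary sets add a condition that is settled later: a recorded use of the product and, for mITT, a follow-up questionnaire as well. Neither condition is part of the stated objective. The protocol confines efficacy data to mITT (12.2.1), but habits reported before treatment are not efficacy data.

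If those who never start, or never return a DHEQ, have different habits from the rest, the reported percentages describe a more selected group than the one enrolled. The data to avoid this are already collected. The stake is one descriptive secondary endpoint. No test or decision rests on it.

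**Working it through.** **1. Who is in which OHQ summary** (set definitions from SAP 4.3.3)

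| Enrolled participant with a completed OHQ | Protocol 12.3.4 (mITT) | SAP 4.3.6 (Safety, mITT) |
|---|---|---|
| No recorded product use | in no summary | in no summary |
| Recorded use, no post-baseline DHEQ Total Score | in no summary | Safety only |
| Recorded use and at least one post-baseline score | mITT | Safety and mITT |

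The first row is missing under both documents. The second row is missing only under the protocol.

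**2. The plan's own figures.** Protocol 12.1 and SAP 4.1 plan about 400 completers with up to 20% dropout: 400 / (1 − 0.20) = 500 enrolled, as stated. No figure is given for the OHQ.

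**3. How many could be left out.** The documents do not say. If the whole planned dropout fell before any post-baseline DHEQ, 0.20 × 500 = 100 people would be outside mITT. That is the worst case within the planned dropout, because one score at any visit keeps a person in mITT. I take 2% to 20% as an assumed range: 0.02 × 500 = 10 to 100 people. The Safety set loses only those with no recorded use, so its share should lie toward the low end.

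**4. Effect on a reported percentage.** Let f be the share of OHQ completers left out, and d the difference in true percentage between those kept and those left out. The percentage in all completers is (1 − f) × kept + f × left out, so the reported figure is off by f × d. With d assumed to be 10, 20 or 30 points:

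| f | d = 10 | d = 20 | d = 30 |
|---|---|---|---|
| 2% | 0.2 | 0.4 | 0.6 |
| 10% | 1.0 | 2.0 | 3.0 |
| 20% | 2.0 | 4.0 | 6.0 |

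The entries are percentage points. The sign is not known.

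**5. Comparison with sampling error.** The 95% half-width for an item near 50% is 1.96 × √(0.25 / n). This gives 4.4 points at n = 500 and 4.9 at n = 400. Only the extreme corner of the table (20% left out, 30-point difference) exceeds the half-width. Using everyone would gain about 0.5 points of precision at most.

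**6. Which denominator.** Protocol 8.2.1 allows 14 days after enrolment to finish the Baseline tasks, so some enrolled people may have no OHQ. The matching set is Enrolled participants with a completed OHQ, not all Enrolled.

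**The case against.** The strongest reply is that the SAP has already closed most of the gap. Its Safety column takes in anyone with a single diary entry, so a participant who brushed once and sent no further DHEQ is counted. This stands, and it narrows the point under the SAP to people with no recorded use.

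It can also be said that Protocol 12.3.4 treats habits together with demographics, where describing the sample behind the efficacy results is normal practice. That justifies keeping the mITT and Safety columns. It does not supply a summary for an endpoint whose stated target is a DH population.

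Third, Enrolled is itself a self-selected group recruited through social media and screened on self-report. This is true. The change removes one selection step and does not make the sample representative.

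A reader might go further and infer three things that the documents do not support:

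- That the summaries describe only people who stayed in the study. Neither set is a completer set, because one recorded use, or one DHEQ score that may come at Week 4, is enough.
- That Baseline answers are thrown away. OHQ responses are listed for Safety. Two OHQ-derived characteristics (dentist diagnosis and sensitivity-toothpaste use) also appear to be listed for Enrolled through SAP 4.3.14.
- That the reported habits will look better than the true ones. Nothing in the documents shows how non-starters brush.

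**Conclusion.** The point holds in a limited form. The OHQ is complete before product ships, yet no planned summary covers every enrolled participant who answered it. The protocol and two sections of the SAP also name different sets for the same data. The shift is 0.2 to 6 points over the assumed ranges. It is probably near the bottom of that range under the SAP's Safety set, and its direction is unknown. These sizes rest on assumed shares and differences, because the documents give neither. The primary analysis and the sample size do not depend on the OHQ set. This is a minor, optional improvement.

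**What to change.** - In Protocol 12.3.4 and SAP 4.3.6, summarise the OHQ endpoint in all Enrolled participants with a completed Baseline OHQ, and show that number in the table header.
- Keep the Safety and mITT columns, labelled as descriptions of the analysed samples.
- Reconcile the OHQ sets across Protocol 12.3.4 (mITT summary), SAP 4.3.6 (Safety and mITT summary, Safety listing) and SAP 4.3.14 (mITT listing). List the OHQ for the same set as the endpoint summary.

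The cost is one extra column in an existing table and a few words in three sections. No new data are needed.

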#### 12.3.5 Study Product Compliance and Use of Other Therapies

#### 12.3.5.1 Study Product Compliance

Compliance with study product usage and with the study schedule will be tabulated and summarized for the Safety population. Summaries will include a simple yes/no frequency (and percent) count at each timepoint:

- Summary of completion to study schedule and assessments (yes/no)
- Summary of product usage according to product instructions (yes/no)
- Summary of number of toothpaste tubes remaining at the end of the study (e.g., '2 or less tubes', '3 to 6 tubes' and 'more than 6 tubes')

#### 12.3.5.2 Prior and Concomitant Medications

Prior and concomitant medications taken during the study will be listed for the Safety population.

## 12.3.6 Handling of Dropouts and Missing Data

Missing data due to dropouts/withdrawals will be assessed on an ongoing basis during the study. Any further sensitivity analyses needed due to missing data will be reviewed at the time of data review.

For the DHEQ data, for any timepoint if response is missing, it will be excluded from the primary analysis; the data available for each participant (even though some time points may be missing) will still be included in the analysis.

The MMRM approach will include all participants in the mITT population in the analysis. Any missing data from such participants will be treated as 'missing at random', i.e., their missing data at a particular time point will be assumed to behave in similar fashion to a participant with non-missing data at that time point who has similar data at other time points. This approach ensures an unbiased approach to handling missing data under the 'missing at random' assumption.

#### 12.3.7 Interim Analysis

No interim analysis is planned for this study.

#### 13 STUDY GOVERNANCE CONSIDERATIONS

#### 13.1 Quality Control

In accordance with applicable regulations including GCP and sponsor procedures, prior to the start of the study, the column virtual site team will be trained on the protocol, study requirements, and their responsibilities to satisfy regulatory, ethical, and sponsor requirements.

Property of Haleon-Confidential

May not be used, divulged, published or otherwise disclosed without the consent of Haleon

When reviewing data collection procedures, the discussion will include identification, agreement, and documentation of data items for which the eCRF will serve as the source document

During the study, the data will be monitored to verify that:

- Data are authentic, accurate, and complete.
- Safety and rights of participants are being protected.
- Study is conducted in accordance with the currently approved protocol and any other study agreements, GCP, and all applicable regulatory requirements.

The extent and nature of monitoring will be described in the Data Management Plan.

## 13.2 Quality Assurance

To ensure compliance with GCP and all applicable regulatory requirements, the sponsor may conduct a quality assurance assessment and/or audit of collection study-related records, and regulatory agencies may conduct a regulatory inspection at any time during or after completion of the study.

In the event of an assessment, audit or inspection, communication must agree to grant the advisor(s), auditor(s) and inspector(s) direct access to all relevant documents and to allocate their time and the time of their staff to discuss the conduct of the study, any findings/relevant issues and to implement any corrective and/or preventative actions to address any findings/issues identified.

will notify the sponsor or its agents immediately of any regulatory inspection notification in relation to the study. Furthermore, will cooperate with the sponsor or its agents to prepare the study site for the inspection and will allow the sponsor or its agents, whenever feasible, to be present during the inspection. will promptly provide copies of the inspection findings to the sponsor or its agents. Before response submission to the regulatory authority, will provide the sponsor or its agents with an opportunity to review and comment on responses to any such findings.

The sponsor will be available to help **CCI** prepare for an inspection.

## 13.3 Regulatory and Ethical Considerations

#### 13.3.1 Institutional Review Board (IRB)

It is the responsibility of **CC** to have prospective approval of the study protocol, protocol amendments, informed consent documents, the safety statement (including any updates) and other relevant documents (e.g., recruitment advertisements), if applicable, from the IRB. All correspondence with the IRB should be retained in **CC** master study file. Copies of IRB approvals should be forwarded to the sponsor prior to the initiation of the study, and also when subsequent amendments to the protocol are made.

The only circumstance in which an amendment may be initiated prior to IRB approval is where the change is necessary to eliminate apparent immediate hazards to the participants. In that event, the investigator must notify the IRB and the sponsor in writing immediately after the implementation.

**HALEON** 

13.3.2 Ethical Conduct of the Study

The study will be conducted in accordance with the protocol and legal and regulatory requirements, as well as the general principles set forth in the International Ethical Guidelines for Biomedical Research Involving Human Subjects (Council for International Organizations of Medical Sciences 2002), International Ethical Guidelines for Health-Related Research Involving Humans (Council for International Organizations of Medical Sciences, 2016), guidelines for GCP (ICH 1996 and revision 2), and the Declaration of Helsinki (World Medical Association 2013).

In addition, the study will be conducted in accordance with the protocol, the ICH guideline on GCP, and applicable local regulatory requirements and laws.

## 13.3.3 Participant Information and Consent

All parties will ensure protection of participant personal data and will not include participant names or other identifiable data in any reports, publications, or other disclosures, except where required by laws.

When study data are compiled for transfer to the sponsor and other authorized parties, participant names, addresses, and other identifiable data will be replaced by numerical codes based on a numbering system provided by the sponsor to de-identify study participants (Note: the use of initials should be avoided).

will maintain a confidential list of participants who participated in the study, linking each participant's numerical code to their actual identity. In case of data transfer, the sponsor will maintain high standards of confidentiality and protection of participants' personal data consistent with applicable privacy laws.

The informed consent documents must be in compliance with ICH GCP, local regulatory requirements, and legal requirements, including applicable privacy laws.

The informed consent documents used during the informed consent process must be reviewed and approved by the sponsor, approved by the IRB before use, and available for inspection.

must ensure that each study participant is fully informed about the nature and objectives of the study and possible risks associated with participation.

#### 13.3.4 Participant Recruitment

Advertisements approved by the IRB may be used as part of the recruitment procedures. Use of an IRB-approved, generic, prescreening questionnaire to assess basic participant characteristics to determine general eligibility for this study is allowed.

The sponsor will have an opportunity to review and approve the content of any study recruitment materials directed to potential study participants before such materials are used.

## 13.3.5 Reporting of Safety Issues and Serious Breaches of the Protocol or ICH GCP

Within the sponsor, a serious breach is defined as a breach likely to affect to a significant degree the safety and rights of a participant or the reliability and robustness of the data generated in Haleon-sponsored human subject research studies.

In the event of any prohibition or restriction imposed (i.e., clinical hold) by an applicable competent authority in any area of the world, or if **COLOMB** is aware of any new information

Property of Haleon- Confidential

that might influence the evaluation of the benefits and risks of the study product, the sponsor should be informed immediately.

In addition, columns will inform the sponsor immediately of any urgent safety measures taken by columns to protect the study participants against any immediate hazard, and of any serious breaches of this protocol or of ICH GCP that columns aware of.

# 13.4 Posting of Information on Publicly Available Clinical Trial Registers

Study information from this protocol will be posted on publicly available clinical trial registers before enrollment of participants begins in accordance with applicable sponsor processes.

The sponsor intends to make anonymized participant-level data from this study available to external researchers for scientific analyses or to conduct further research that could help advance medical science or improve patient care. This helps ensure the data provided by study participants are used to maximum effect in the creation of knowledge and understanding

## 13.5 Provision of Study Results to the Investigator

Where required by applicable regulatory requirements, an investigator signatory will be identified for the approval of the Clinical Study Report (CSR). College will be provided reasonable access to statistical tables, figures, and relevant reports and will have the opportunity to review the complete study results at a sponsor site or other mutually agreeable location.

The sponsor will also provide **CCI** with the full summary of the study results. is encouraged to share the summary results with the study participants, as appropriate.

The procedures and timing for public disclosure of the results summary and for development of a manuscript for publication will be in accordance with sponsor policy.

A manuscript will be progressed for publication in the scientific literature if the results provide important scientific or medical knowledge.

#### 13.6 Records Retention

Following closure of the study, columns must assure that the participant's anonymity will be maintained. eCRFs or other documents submitted to the sponsor should not identify participants by their names or initials but by an identification code. CCI should keep a separate log of participant codes, names and addresses. Documents not for submission to the sponsor should be maintained by cci in strict confidence.

must maintain all site study records (except for those required by local regulations to be maintained elsewhere) in a safe and secure location.

study records (eTMF) must be maintained to allow easy and timely retrieval, when needed (e.g., for a sponsor audit or regulatory inspection) and must be available for review in conjunction with assessment of the facility, supporting systems, and relevant study staff.

Where permitted by local laws/regulations or institutional policy, some or all, of these records can be maintained in a format other than hard copy (e.g., microfiche, scanned, electronic); however, caution needs to be exercised before such action is taken.

must ensure that all reproductions are legible, are a true and accurate copy of the original, and meet accessibility and retrieval standards, including re-generating a hard copy, if

Property of Haleon- Confidential

May not be used, divulged, published or otherwise disclosed without the consent of Haleon

required. Furthermore, collections must ensure there is an acceptable back-up of these reproductions and that an acceptable quality control process exists for making these reproductions.

Records and documents, including signed eIC, pertaining to the conduct of this study must be retained by CCI as as per the signed contractual agreement, from the issue of the final CSR or equivalent summary, unless local regulations or institutional policies require a longer retention period. The minimum retention time will meet the strictest standard applicable to that site for the study, as dictated by any institutional requirements or local laws or regulations, sponsor standards/procedures, and/or institutional requirements.

No study document should be destroyed without a prior written agreement between the sponsor and columns. Columns must notify the sponsor of any changes in the archival arrangements, including, but not limited to, archival at an off-site facility or transfer of ownership of the records in the event columns is no longer associated with the site.

